#### 2.5 Study design

This is a phase IIa, Triple-blind, sham-controlled randomised trial of superiority (stimulation is superior to sham treatment).

#### 2.6 Study setting

This is a single centre UK study taking place within Barts Health NHS Trust. Provision of mechanical thrombectomy is the only site-specific requirement to run the study. Potential participants will be identified through two possible routes: 1) when referrals for mechanical thrombectomy are made by the stroke consultants or 2) from outside referring secondary care, NHS hospital centers.

# 3.0 Patient Evaluability and Replacement

Withdrawn participants will not be replaced (intention to treat analysis).

#### 3.1 Target Accrual

36 participants undergoing mechanical thrombectomy will be recruited.

#### 3.2 Participant identification and recruitment

The stroke consultant (direct care team) receiving referrals for mechanical thrombectomy will screen potential participants for eligibility at the hospital site. Once eligibility is established, the stroke medicine consultant will confirm with the interventional radiology consultant the participant is eligible to enter the trial. The eligibility confirmation will be documented in the medical records prior to randomisation. Participants that undergo screening and meet the inclusion criteria will be recorded on the study screening log stored in the investigator site file. Only anonymised screening data will be collected by the central trial coordinating team for publication purposes. After provision of written consent, the patient has been enrolled in the study and recorded on the study enrolment log with their trial ID.

# 4.0 Informed consent procedures

Patients presenting with acute ischaemic stroke are frequently unable to consent for themselves due to neurological impairment, sedation or delirium. For every 30-minute delay, the odds of achieving a good outcome are reduced by 50% from initial confirmation of stroke to thrombectomy achieving reperfusion. (PMID: 26956258) Therefore, due to the emergency clinical situation, VANS will adopt a research without prior consent (also referred to as deferred consent) where eligible patients will be enrolled in the study through consent from a Professional consultee who would be the named interventional radiology consultant in charge of the patient's thrombectomy care. The consultant will be asked to sign the Consultee Declaration Form. The consultant retains one copy of the form; one copy goes in the participant's medical notes and the third in the investigator site file.

The Principal Investigator retains overall responsibility for the informed consent of participants at their site and must ensure that any person delegated responsibility to participate in the informed consent process is authorised, trained and competent to participate according to the protocol and standards set by GCP. Delegation can only be to medically qualified research team members.

Following participant enrolment, a delegated member of the site research team will approach the patient's Personal consultee if available. This may be a family member, partner or friend. This Personal consultee will be fully informed about the trial by a member of the research team or the responsible clinician. Personal Consultees will be given a copy of the Personal Consultee Information Sheet. They will be asked to provide their opinion as to whether the patient would object in taking part in medical research. If they decide that the patient would not object they will be asked to sign the appropriate informed consent form. Two copies of this form will be made — one copy in the medical records, original in the investigator site file and one left with the representative.

If a Personal Consultee advises that, in their opinion, the patient would not choose to participate in the trial, then the trial treatment will be stopped (if ongoing). The Personal Consultee will be asked whether, in their opinion, the patient would be willing to continue with ongoing data collection. If a Personal consultee is not available during the trial period, the data collected will be retained and the seven day follow-up data will be collected from reviewing the patients medical records at Barts NHS Trust.

In cases where consent has been given by a Personal or Professional consultee, the patient will be informed of their participation in the study as soon as they have return of capacity. If the patient has regained capacity during their stay in Barts NHS Trust, a member of the research team will meet with them and explain the study and provide a copy of the patient information sheet. The patient will need to sign a copy of the informed consent form. One signed copy will be retained by the patient, one placed in the medical notes and one in the study site folder. If participants decline to participate in the trial, consent will be sought to retain and analyse their data and samples collected so far.

If the patient does not regain capacity during their stay at Barts NHS Trust and transferred, to another hospital without providing consent a covering letter notifying them of their participation in the trial, participant information sheet and consent form will be sent with their medical notes.

On the occasions patients have regained capacity and are discharged before being approached by the research team they will be contacted in the first instance by phone. If the research team do not get a response to at least three telephone call attempts, then the patient will be approached by post a maximum of twice. The patient will be sent a covering letter and a copy of the patient information sheet and consent form. The letter will direct the patient to the participant information sheet for detailed information on the trial and provide contact details for if the patient wishes to discuss the trial further.

The right of a participant to refuse participation without giving reasons will be respected. The participant will remain free to withdraw at any time from the study without giving reasons and without prejudicing their further treatment and will be provided with a contact point where they may obtain further information about the study. Where a participant is required to re-consent (for example if new Research Safety Information becomes available during the study, or following an amendment that affects the participant, or new information needs to be provided to a participant) it is the responsibility of the PI to ensure this is done in a timely manner and prior to the next use of the investigational device (where applicable).

Patients who are consented but not entered into this study should be recorded (including reason not entered) on the screening log in the Investigator Site File (ISF). Original signed consent forms will be kept by the investigators and a copy will be given to the participant or representative.

#### 4.2 Vulnerable participant considerations

The study will involve the participation of vulnerable participants, as adults with acute ischaemic stroke are frequently not able to consent for themselves. The PI is responsible for ensuring that all vulnerable participants are protected and participate voluntarily in an environment free from coercion or undue influence.

#### 4.3 Writing, reading, and translation considerations

If verbal translation is needed, an NHS hospital interpreter will be provided.

#### 4.4 Participants lacking capacity

Participants presenting with acute ischaemic stroke frequently lack the capacity to consent for themselves. Please see above section for description of process. If a participant is able to consent for a Clinical Investigation but later becomes incapacitated, the original consent given endures the loss of capacity, because the study has not significantly altered.

# 4.5 Consent for ancilliary studies

Informed consent will be obtained from participants for their blood samples to be used for any future research associated with the trial.

#### 5.0 Participant eligibility criteria

#### 5.1 Inclusion criteria

- Age 18 years and over
- Requiring mechanical thrombectomy for acute ischaemic stroke under general anaesthesia and/or sedation
- Established hypertensive and/or hypertensive on admission for mechanical thrombectomy (systolic BP >140mmHg; diastolic BP >80mmHg)

#### 5.2 Exclusion criteria

- Refusal to provide informed consent
- Current participation in a clinical trial of a treatment with a similar biological mechanism.
- Previous enrolment into VANS trial.
- Anatomical or other contraindication to non-invasive transcutaneous autonomic neuromodulation (see Investigator Brochure appendix D).
- Pregnancy.

# 6.0 Study Schedule

#### 6.1 Schedule of treatment for each visit

# Visit 1 (eligibility check and consent before mechanical thrombectomy)

- On referral for mechanical thrombectomy, potential participants will be screened for eligibility
  and if suitable informed consent will be obtained. Please see section 4 for further details on
  informed consent procedures.
- Routine pre-procedure serum pregnancy test for female participants will be checked.

 Demographic information, medical history, current concomitant medication, NIHSS will be recorded.

# Visit 2 (day of mechanical thrombectomy)

- Following informed consent, participants will be randomised to either the active stimulation or sham arm and assigned a trial ID.
- Heart rate data will be captured by dedicated Holter monitors.
- Blood samples will be collected before the start of mechanical thrombectomy.
- Before the sterile mechanical thrombectomy field is prepared, the AffeX-CT device will be applied to each ear for the duration of the mechanical thrombectomy procedure. Leads will be placed on each ear in the tragus area of the outer ear. The device will be preset to deliver either sham or active TAN. The ear leads will remain attached for the duration of the thrombectomy procedure which is typically two hours and removed at the point the patient leaves the radiology suite to be taken to the post recovery anaesthetic room.

#### Visit 3 (day after mechanical thrombectomy)

- The AffeX-CT device will be applied to each ear for typically one hour during this period
- Heart rate data will be captured by dedicated Holter monitors.
- Study data will be collected including concomitant medication and NIHSS will be recorded.
- Blood samples blood will be collected after the one hour stimulation period.
- Blood pressure data will be downloaded from the electronic health record and stored securely within QMUL/Barts Health NHS Trust for subsequent analysis.

# Visit 4 (seven days after mechanical thrombectomy)

• Patient vital status will be checked (alive/ dead/ in-hospital)

# 6.2 Schedule of assessment

Event/Visit	Screening	Day of MT*	Morning after MT	24 hours after MT*	Day 7 after MT*
Inclusion/exclusion	х				
Heart rate and blood pressure safety review		х		x	х
Informed Consent (professional/ personal)		х		х	
Informed Consent (patient)					х
Randomisation		х			
Heart rate		х	х		
Blood pressure		x		x	
Investigational procedure: TAN		х	х		
Medical record review	х	х		х	х
Trial blood sample		х		х	
Follow-up					х
Safety review		х		x	x

\*MT: Mechanical thrombectomy

#### **6.3 Randomisation procedure**

Randomisation will occur on the day of mechanical thrombectomy after informed consent but before the procedure is due to start. Participants will be centrally allocated to either sham or active stimulation in a 1:1 ratio with block randomisation. No minimisation is required. The allocation sequence is generated and validated by the Statistician which will then be provided to the device manufacturer (Afferent) to program the simulators accordingly. The allocation sequence will be concealed to all trial investigators. The stimulators will be numbered sequentially starting at 1, and programmed according to the random allocation sequence provided. There will not be a possibility to identify the treatment group by any markings on the stimulator boxes.

To register a patient into the VANS trial, research staff at the site will log on to a secure data entry platform hosted by Queen Mary University of London and complete the patient's details to obtain a unique patient identification number. The patients will be allocated to a sequential trial group ID corresponding to the stimulator box, starting with 1, then 2 and so on. All details of the eligibility screening process including participants who are screened and not randomised will be documented in the medical records.

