#### 6.4 Blinding

This is a triple-blind trial, with trial participants, care providers and endpoint assessors to the treatment group allocation. The primary outcome will be analysed by individuals masked to the patient treatment allocation and clinical outcomes. Afferent Medical Solutions Ltd will be unblinded to facilitate reporting of Serious Adverse Device Events (SADE) or Unexpected Serious Adverse Device Events (USADEs) to the MHRA. The blinded interventions are highly comparable, as the same device will be used for all participants randomized to either active stimulation or turned off. Final unblinding of all study participants will occur after the data set is locked.

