#### 6.5 Unblinding

Unblinding a participant's treatment is strongly discouraged as it can compromise the integrity of the trial. However, unblinding may be necessary on rare occasions for medical or safety reasons that can affect clinical management. In this trial, unblinding may be required if a patient experiences a cardiac arrhythmia of concern to attending clinicians. The PI or assigned delegate must determine the necessity of unblinding, and contact the study coordinating team for further discussion. Healthcare professionals will be provided with emergency contact details of the research team to quickly unblind a participant if knowledge of the treatment assignment is essential for optimal medical treatment. A 24-hour emergency unblinding procedure will be available, and participants will receive a trial card with emergency contact details. Unblinding requests are expected to be rare as the rescue treatment should not depend on the treatment group allocation.

To ensure the safe unblinding of information in case of a safety concern, we will store unblinding details in a securely locked cupboard that can be accessed by the research/clinical team with prior discussion and approval from the PI or their designated representative. The cupboard will be accessible at all times. Unblinding information will be contained in opaque sealed envelopes that will be labelled with the corresponding stimulator box number and contain treatment group allocation (stimulation or sham) inside. The Statistician will be responsible for inserting the treatment group information and sealing each envelope, which will be witnessed and verified by an independent staff member not involved in the trial. This process will ensure that the treatment group allocation cannot be viewed without opening the sealed envelope. To enhance the security and confidentiality of the unblinding process, each envelope will be signed by the Statistician on the back, and they can be examined at the end of the trial to verify that none of them have been tampered with. The envelopes will be kept in a designated folder that is labelled clearly, and this folder will be stored in a securely locked cupboard that can be accessed at any time of the day. The Statistician and the witness will sign a file note that outlines the process used to create and seal the envelopes.

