#### 14.6 Procedure(s) to account for missing or spurious data

As the primary outcome uses routinely captured data stored by Barts Health EPR, there is minimal risk of missing blood pressure-related data. Heart rate data will be captured by dedicated Holter monitors provide by the Chief Investigator. Any missing data will not be inputed. Sensitivity analyses to assess the robustness of study results if there are missing primary outcome data will be undertaken. This pilot study will assess data completeness to inform decisions about missing data for a future main trial. Analysis will use all participants with available endpoint data. The level of missing data will be tabulated for each outcome, presenting the number of subjects with a data record and number with missing data, separately by trial arm. Each endpoint will be analysed on a complete case basis. For continuous variables, distributional assumptions will be hard to assess with the small sample size for this pilot study. However, if any continuous endpoint variables appear to seriously violate distributional assumptions or very extreme outliers observed, then non-parametric alternative approaches to analysis will be undertaken in such cases.

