#### 15.5 Data Management

Source data verification will be conducted in the eCRF. Final sign-off by the site Principal Investigator will be undertaken. A single final data lock will prevent changes, to protect the final data set. The final dataset will be exported from the study database for analysis by the trial statistician. A trial specific Data Management Plan will be developed by the Coordinating team detailing all key methods of data management for collecting, recording and handling of trial data.

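### Section 6.4 promises a masked primary analysis, but the roles as written appear to let the analysing statistician know or recover allocation before data lock

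*Protocol*

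**What the plan says.** **The masking claim.** Protocol 6.4 states: "The primary outcome will be analysed by individuals masked to the patient treatment allocation and clinical outcomes". It adds: "Final unblinding of all study participants will occur after the data set is locked". The one party it identifies as unblinded is the manufacturer, for safety reporting.

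**Who makes and handles the list.** Protocol 6.3: "The allocation sequence is generated and validated by the Statistician". The list then goes to the manufacturer, who programs numbered stimulators. Concealment is described for one group only: "The allocation sequence will be concealed to all trial investigators". Protocol 6.5: "The Statistician will be responsible for inserting the treatment group information and sealing each envelope", with an independent person outside the trial as witness. Each envelope carries the box number.

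**How patients are tied to the list.** Protocol 6.3: "The patients will be allocated to a sequential trial group ID corresponding to the stimulator box", beginning at 1 and running upwards.

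**Who analyses.** Protocol 15.5: "The final dataset will be exported from the study database for analysis by the trial statistician". Protocol 14.0 also gives the statistician any safety analysis that the steering committee requests during recruitment.

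**What the SAP adds.** Its first page lists one trial statistician alongside the Chief Investigator. Its Administrative information section says that version 1.0 was written before the author had seen unblinded data, defined as the dataset with the allocation variables in it.

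**The concern.** Masking the analyst protects decisions taken after the data are seen: which readings are implausible, what counts as an outlier, which test is used. It works only if the person taking those decisions does not know the arms. Someone who built a list keyed to box number, and who then receives data from patients who took boxes in order, does not need an allocation variable in the export to know or work out who had stimulation.

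Two things are at stake. Data-dependent choices on the primary outcome could be made by someone able to know the allocation. And the final report could repeat a safeguard from 6.4 that the described roles do not deliver.

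**Working it through.** The plan gives no figure to reproduce, so the check sets the sections side by side.

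1. **Does the person who makes the list know it?** Yes. The Statistician generates and validates it (6.3) and places each allocation in its envelope (6.5). Witnessed sealing guards against tampering; it does not remove what the sealer knows.

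2. **Is that person the analyst?** This step is inferred. Sections 6.3 and 6.5 refer to the Statistician, and 15.5 to the trial statistician. No section says that they are the same person. In favour of the inference, the SAP lists a single statistician and neither document describes a separate list-holder. The only other statisticians mentioned sit on the steering committee (23.2) and the data monitoring committee (23.3), and neither is given the list or the analysis.

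3. **Can the list be linked to patients?** Very probably. The sequential group ID matches the box (6.3). No section says that this ID is in the analysis export, and 6.3 describes a separate unique patient number. However, 6.6 collects the dates of consent and of thrombectomy, and boxes are issued in order. Enrolment order would therefore recover most or all of the sequence.

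4. **Does the SAP statement close the gap?** No. It concerns access to a dataset containing allocation variables. Someone holding the list could make that statement truthfully. It also covers the writing of the SAP, not later cleaning and analysis.

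5. **Does the data lock close it?** Only in part. The single final lock (15.5) prevents changes to the dataset, and general unblinding follows it (6.4). Neither removes earlier knowledge of the list, and the lock is not said to cover the derived outcome, exclusions, test or code.

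6. **What is still open to judgement on the primary outcome?**
   - *Spurious readings:* Protocol 14.6 has them in its title but gives no rule. Appendix A sets no requirement on the number of readings.
   - *Choice of test:* if a variable looks badly non-normal or has very extreme outliers, "then non-parametric alternative approaches to analysis will be undertaken" (14.6). No threshold is given.
   - *Model:* Protocol 14.3 names repeated measures ANOVA; the SAP's primary analysis section names no model.
   - *Covariates:* Protocol 14.2 plans adjusted differences and the SAP refers to covariates in the model; neither lists them.

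7. **What is already fixed?** The coefficient of variation is 100 × SD / mean (SAP Appendix 1). The readings are routine-care measurements from the electronic record. Missing outcomes are not imputed, and each endpoint is analysed on complete cases (14.6).

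**The case against.** The strongest reply is that 6.4 may not be about the statistician. It speaks of people in the plural who are masked to clinical outcomes as well as to allocation. The trial statistician will handle NIHSS, arrhythmia and troponin data and so can hardly be masked to those. The sentence might mean the staff who derive blood pressure variability from the downloaded records. The blinded parties that 6.4 lists are participants, care providers and endpoint assessors, not the statistician. On that reading the wording is unclear rather than contradictory.

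This is a fair reading, but it does not settle the matter. The sentence says that the outcome is analysed by masked people, and 15.5 gives analysis of the final dataset to the trial statistician. A reader of the report would take the claim to cover the treatment comparison. If it covers derivation only, 6.4 needs to say so.

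A second reply is that the vague non-parametric switch would be a weakness even with a masked analyst, since unblinding after lock is planned. That is true: it is a gap in its own right. It matters here because masking would otherwise be the protection against its misuse.

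A third is that the lock, the fixed formula and the complete-case rule already limit the harm. That stands, and it limits the weight of the point.

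**Conclusion.** The point holds as a mismatch between a stated safeguard and the roles described. Section 6.4 asserts a masked primary analysis. The other sections, taken together, appear to let the analyst know or recover allocation before lock.

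A reader might go further and conclude that one person certainly does everything, that all 36 allocations are known to the analyst, and that masking is absent. The documents do not support that as fact. The shared identity is a strong inference, not a statement; the box ID is not said to be in the export; and 6.4 may have other staff in mind. Nor does anything suggest misconduct.

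If the roles are shared, the arms of all 36 patients are in principle open to the analyst. The resulting bias cannot be quantified from the documents. Its scope is limited by a fixed formula on routine readings and a set rule for missing outcomes. What remains exposed is the handling of spurious readings and outliers, the choice of test, and the unspecified model and covariates. That is enough to warrant correcting the text before results are reported, though not to question the design.

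**What to change.** 1. **State the roles.** In 6.3 to 6.5 and 15.5, say whether the list-holder and the analyst are the same person, and who is masked until when.

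2. **If they are the same person,** amend 6.4 to say that the analysing statistician is not masked, and do not describe the analysis as masked in the report. This still works if the list already exists.

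3. **If an existing statistician who will not analyse the data is available,** assign that person to generate the list and seal the envelopes. Keep the independent witness as witness only; having the witness run the randomisation code would remove the second-person check in 6.5.

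4. **In either case,** before allocation is merged, date and lock the cleaned blood pressure file, the derived coefficient of variation, the decisions on spurious readings and outliers, the choice between parametric and non-parametric test, and the analysis code. If the analyst holds the list, this does not create masking, but it puts the decisions on record before any comparison is run.

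5. **Reconcile one related statement.** The SAP's randomisation procedure says that the allocation is shown to whoever randomises; Protocol 6.3 describes only a number matched to a box.

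The cost is a small amount of documentation and, under option 2, a less favourable masking statement. Disclosure and the lock need no new staff; option 3 depends on a suitable statistician already being available. Sample size, endpoints and patient procedures are unaffected.
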